Primary outcome (week 8)	 a. Cohort 1: Any vehicle trip in past 2 weeks where individual reports not using a seat belt b. Cohort 2: Any vehicle trip in past 2 weeks where individual reports phone was used to type while driving and car was moving

	 Cohort 3: Any vehicle trip in past 2 weeks where individual reports driving a vehicle within 3 hours after consuming 3 or more drinks
Key secondary outcomes	Effectiveness-Primary outcomes at week 14 (durability)Feasibility-Percentage of ED patients who screen positive and agree to enrollPercentage of ED patients who enroll who meet run-in criteria.Acceptability-Percentage of ED patients enrolled in the Intervention arm who complete at least 50% of the SMS assessments during the intervention periodPercentage of ED patients enrolled in the Intervention arm who found the program helpful.

STEERING COMMITTEE

[name].

Assistant Professor of Emergency Medicine University of Pittsburgh School of Medicine

[name].

Assistant Professor of Emergency Medicine University of Pennsylvania School of Medicine

[name]

American College of Emergency Physicians Emergency Medicine Foundation

[name].

Assistant Professor of Nursing University of Pennsylvania School of Medicine

[name] , Ph.D.

[name] of Michigan

[name]

Director of Grant Development American College of Emergency Physicians Emergency Medicine Foundation

Conflicts of interest

The members of the steering committee have no financial conflicts of interest related to the current trial.

TRIAL SITES

Coordinating Center University of Pittsburgh

Department of Emergency Medicine Site Investigator: [name]

Enrolling Sites*

Hospital Name	Location	Site Principal Investigator
UPMC Mercy Hospital	Pittsburgh, PA	[name]
UPMC Passavant Hospital	McCandless, PA	[name]
Hospital of the University of Penn	Philadelphia, PA	[name]
Penn Presbyerian Hospital	Philadelphia, PA	[name]

*Depending on study progress, sites may be added or removed in the future.

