2.14 Outcome Assessments & Blinding

The primary outcomes will be the percentage of participants in each treatment arm who report vehicle risks at week 8 (immediate effects) and week 14 (durable effects). Questions are the same as those used in screening. Participants will receive a text prompting them to log in to the secure web site to complete the 21-question survey which should take them no more than 10 minutes to complete. Research associates and investigators will be blinded to the allocation until outcome evaluation. It is not possible to blind subjects given the nature of the intervention. We do not expect any scenarios where emergency unblinding will be necessary.

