4.2.2 Primary Analysis

At baseline, all participants (based on screening criteria) all had the risk factor. At subsequent time points, participants are analyzed as having/not having the same risk factor by randomized group. For our primary analysis, we will examine the proportion of participants in each group (SMS intervention; assessment control) who report the risk behavior using a chi-squared test of proportions. We will then perform a logistical regression, entering any baseline attribute that has univariate association with the outcome in the final model. We will report the difference in percentage with primary outcomes as well as odds ratios (from logistical regressions) with 95% confidence intervals The α level is set at .05 for all statistical tests.

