4.2.3 Secondary Analyses

The percentage of ED patients who screen positive and agree to enroll, the percentage of ED patients who enroll who meet run-in criteria, the percentage of ED patients enrolled in the Intervention arm who complete at least 50% of the SMS assessments during the intervention period, and the percentage of ED patients enrolled in the Intervention arm who found the program helpful will be calculated and presented with 95% confidence intervals. We will explore whether individual factors (e.g. sex, race, education) are associated with enrolling, meeting run-in criteria, completing SMS assessments or finding the program helpful using multi-level modeling. We will examine whether perceived norms, perceived control, or perceived risk differed between treatment arms. We will explore the slope of change over time in SMS risk reports using generized estimating equations (GEE) with log link function, examining time, treatment and time*treatment effects. Any individual factors signifianctly associated with SMS assessment completion will be included as

covariates.GEE is the recommended technique to handle non-parametric residuals and missingness associated with repeated-measured data. We will use robust estimates and account for clustering of outcome data within individuals. Results will be presented as odds ratios with 95% confidence intervals.

Handling Missing Outcome Data: If a participant is missing outcome assessment time points (week 8 or week 14), vehicle risk behavior will be imputed based on a pre-defined plan as follows. If a participant has reported that risk via SMS weekly reports, we will use those values for missing weeks. If either of the prior 2 weeks is missing on both web-based recall report or SMS reports, we will impute the missing week based on the worst performance recorded in the weeks either before or after the missing one using SMS values. We believe that this will provide the most conservative estimate of the missing value. Sensitivity analyses will be performed using various other imputation techniques, including multiple chained imputations using baseleine and prior SMS reports.

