5.2 Variables

Measure library is included in the Appendix.

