Appendix: Screening Questions

Question	How old are you?	18 years old	19 years old	20 years old	21 years old
Code	age	0	1	2	3
Question	What is your sex?	Female	Male		
Code	sex	0	1		
Question	Are you Hispanic or Latino?	No	Yes		
Code	hisp	0	1		
Question	What is your race? (Select one or more responses.)	Black or African American	White	Asian	Other
Code	brace, wrace, asian, rother	0/1	0/1	0/1	0/1
Question	Are you currently enrolled in school?	No	Yes, High School	Yes, College	
Code	school	0	1	2	
	The following questions ask you to recall times you have been in a car over the past 2 weeks.				
Question	How often have you driven a car?	Never	A few times	Most	Every
Code	driver	0	1	days 2	day 3
Question	How often did you wear a seat belt when you drove a car?	Never	A few times	Most of the time	Always
Code	drive_seatbelt	0	1	2	3
Question	How often have you been a passenger in the front seat of a car?	Never	A few times	Most days	Every day
Code	pass_front	0	1	2	3
Question	How often did you wear a seat belt when you were a passenger in the front seat ?	Never	A few times	Most of the time	Always
Code	pass_seatbelt1	0	1	2	3
	How often have you been a passenger in the back seat of a car?	Never	A few times	Most days	Every day
	pass_back	0	1	2	3
	How often did you wear a seat belt when you were a passenger in the back seat?	Never	A few times	Most of the time	Always
	pass_seatbelt2	0	1	2	3
Question	How often did you type on your phone while you were driving and when the car was moving?	Never	A few times	Most of the time	Always
Code	distract	0	1	2	3
Question	Have you driven a vehicle within 3 hours after consuming 3 or more alcoholic drinks?	No	Yes		
Code	drinks	0	1		
	Thanks! Please hand the iPAD back to the Researcher.				

RA enters code: SAVE

Program displays which risks+

Script RA tells pt they are potentially eligible for study or thanks them for their time.

If eligible pt interested, RA asks the following:

Question	Do you have a personal cell phone with text messaging ?	No	Yes
Code	sms	0	1
Question	Do you plan to drive and/or ride in a vehicle in the next month?	No	Yes
Code	future	0	1
Question	Do you plan to change phone numbers in the next 3 months?	No	Yes
Code	phone	0	1

Logic If sms=0 or future=0 or phone=1, they are excluded.

RA either thanks them for their time or starts informed consent.

RA goes to WebDataXpress site

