Appendix: 8-Week Assessment

	been in a car over the past 2 weeks.				
Questi on	How often have you driven a car?	Never	A few times	Most days	Every day
Code	driver	0	1	2	3
Questi on	How often did you wear a seat belt when you drove a car?	Never	A few times	Most of the time	Always
Code	drive_seatbelt	0	1	2	3
Questi on	How often have you been a passenger in the front seat of a car?	Never	A few times	Most days	Every day
Code	pass_front	0	1	2	3
Questi on	How often did you wear a seat belt when you were a passenger in the front seat ?	Never	A few times	Most of the time	Always
Code	pass_seatbelt1	0	1	2	3
Questi on	How often have you been a passenger in the back seat of a car?	Never	A few times	Most days	Every day
Code	pass_back	0	1	2	3
Questi on	How often did you wear a seat belt when you were a passenger in the back seat?	Never	A few times	Most of the time	Always
Code	pass_seatbelt2	0	1	2	3
Questi on	How often did you type on your phone while you were driving and when the car was moving?	Never	A few times	Most of the time	Always
Code	distract	0	1	2	3
Questi on	What's the most number of alcoholic drinks you've had prior to driving on any occasion?	#			
Code	drinks	#			

The following questions ask you to recall times you have been in a car over the past 2 weeks.

Questi on	Check off all the reasons you have not used a seat belt	Uncomfort able	Forgot	Don't think they help	Like freedom	Other	l alway s wear my seat belt	
Code	seatbelt reasons	0	1	2	3	4	5	
Questi on	lf other, state reasons							
Code	seatbelt_other							
Questi on	How often do your friends use their seat belt?	Never	Rarely	Most of the time	Always			
Code		0	1	2	3			
Questi on	How dangerous is it to not wear a seat belt?	Not at all	Somew hat	Very	Comple tely			
Code	danger_seatbelt	0	1	2	3			
Questi on	How much do you agree: I have complete control over whether I wear a seat belt.	Strongly Disagree	Disagre e	Somew hat Agree	Mostly agree	Stron gly Agree		
Code	control_sb	0	1	2	3	4		
Questi on	Check off all the reasons you have typed on your phone while driving?	l could not wait	l don't think it affects my driving	It was an emerge ncy	It is fun	l get bored drivin g	l do not use my phon e while drivin g	l do not dri ve
Code	twd reasons	0	1	2	3	4	9 5	6
Questi on	How often do your friends type on their phones while driving?	Never	Rarely	Most of the time	Always			
Code		0	1	2	3			

SaVE Trial Protocol v.1.0 Page **33** of **36**

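### The week-8 and week-14 surveys do not ask Cohort 3's primary-outcome question: they collect a drink count with no 3-hour window and no scoring rule

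*Combined protocol and SAP*

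**What the plan says.** The Synopsis and section 3.1.1 give Cohort 3 a binary primary outcome at week 8: "Any vehicle trip in past 2 weeks where individual reports driving a vehicle within 3 hours after consuming 3 or more drinks". Section 3.1.4 repeats the outcome at week 14 to assess durability.

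Section 2.14 states that both assessments are web surveys and that "Questions are the same as those used in screening". Section 4.2.2 carries this into the analysis: at later time points "participants are analyzed as having/not having the same risk factor by randomized group", compared by chi-squared test. For the wording of the items, section 5.2 says "Measure library is included in the Appendix".

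The screening questionnaire asks "Have you driven a vehicle within 3 hours after consuming 3 or more alcoholic drinks", answered No or Yes and stored as 0/1 under the code `drinks`. The 8-week and 14-week surveys use the same code for "What's the most number of alcoholic drinks you've had prior to driving on any occasion", answered with a number.

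For a missing survey, section 4.2.3 turns to the weekly texts: "If a participant has reported that risk via SMS weekly reports, we will use those values for missing weeks". If a week is missing there too, it takes the "worst performance recorded in the weeks either before or after the missing one using SMS values".

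**The concern.** The outcome has three elements: a 2-week recall period, a threshold of 3 drinks, and driving inside a 3-hour window. The follow-up item keeps the first through the survey heading, leaves the second to a cut-off nobody has specified, and drops the third. Someone who has four drinks in the evening and drives the next morning reports a count of 4 without having met the definition. Section 3.2.4 justifies the 3-hour, 3-drink rule as a marker of a likely blood alcohol level, and the count loses that rationale.

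Three things follow.

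- The planned test would not compare the arms on Cohort 3's stated outcome for anyone who completes the survey.
- Responders and non-responders could be scored on different constructs within one variable.
- With no scoring rule, the cut-off could be chosen after the data are seen.

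Cohort 3 is exploratory (section 2.1), but it has its own primary outcome, and section 10 plans a separate main manuscript for it.

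**Working it through.** **Wording, side by side**

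| Source | Drink-driving item | Answer | 3-hour window | 3-drink threshold |
|---|---|---|---|---|
| Section 3.1.1 (definition) | any such trip in 2 weeks | yes/no | yes | yes |
| Screening, code `drinks` | same behaviour | 0/1 | yes | yes |
| Run-in texts, drink driving | same behaviour | Yes/No | yes | yes |
| Intervention texts, drink driving | same behaviour | Yes/No | yes | yes |
| 8-week survey, code `drinks` | largest number of drinks before driving | number | no | no |
| 14-week survey, code `drinks` | largest number of drinks before driving | number | no | no |

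The seat-belt and typing items are the same at screening, week 8 and week 14, so only Cohort 3's item changed. No section converts the count to yes/no. An accurately reported count below 3 rules the outcome out; a count of 3 or more leaves it undetermined. No text script is shown for controls after the run-in or for weeks 9 to 14, so the 3-hour wording there is inferred.

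**The plan's own figure**

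The only calculation in the plan is for Cohort 1. For 25% vs 10%, two-sided 0.05 and 80% power, the two-proportion formula gives 100 per group, and 300 × 0.9 × 0.8 = 216. Both match section 4.1. There is no Cohort 3 figure to reproduce.

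**Illustration of the consequence**

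None of these inputs is in the documents except the 15-point gap, which is borrowed from Cohort 1. Assume the count is cut at 3 or more and true risks are p = 0.60 (control) and 0.45 (intervention). With sensitivity Se and specificity Sp,

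observed risk = p·Se + (1 − p)(1 − Sp).

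If Se and Sp are equal in the two arms, the observed difference is 0.15 × (Se + Sp − 1).

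| Se | Sp control | Sp intervention | Control | Intervention | Difference (points) |
|---|---|---|---|---|---|
| 1 | 1 | 1 | 60.0% | 45.0% | 15.0 |
| 1 | 0.9 | 0.9 | 64.0% | 50.5% | 13.5 |
| 1 | 0.7 | 0.7 | 72.0% | 61.5% | 10.5 |
| 1 | 0.5 | 0.5 | 80.0% | 72.5% | 7.5 |
| 0.9 | 0.9 | 0.9 | 58.0% | 46.0% | 12.0 |
| 0.9 | 0.7 | 0.7 | 66.0% | 57.0% | 9.0 |
| 0.9 | 0.5 | 0.5 | 74.0% | 68.0% | 6.0 |
| 1 | 0.8 | 0.7 | 68.0% | 61.5% | 6.5 |
| 1 | 0.7 | 0.8 | 72.0% | 56.0% | 16.0 |

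Example, second row: 0.60 + 0.40 × 0.1 = 0.640 and 0.45 + 0.55 × 0.1 = 0.505, a difference of 0.135.

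The rows with equal Sp and Se = 1 isolate the lost 3-hour window. Those with Se = 0.9 add under-reporting, which the Yes/No item could suffer as well. The last two show that dilution is not guaranteed. One way specificity could differ by arm (an inference) is that intervention participants learn to wait longer before driving: they then avoid the defined outcome but still report a high count.

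The number of participants affected is not estimated. Section 4.2.1 limits the analysis to those with at least one text response in the intervention period, and the documents do not say how many that leaves.

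**Separate item**

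The item coded `control_dd` sits among the drink-driving questions but repeats the phone-typing text at baseline, week 8 and week 14. Perceived control over drink driving is therefore never measured, although section 4.2.3 compares perceived control between arms and section 4.2.4 defines a subgroup by it.

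**The case against.** The case for leaving this low on the list has several parts.

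- **Cohort 3 is small and exploratory.** Even if all 100 enrolled were analysed (50 per arm), the assumed 60% vs 45% gives about 32% power with a perfect item, and about 27%, 20% and 14% at common specificities of 0.9, 0.7 and 0.5 with perfect sensitivity. The test is weak either way. This stands and caps the severity, but it does not make the item valid.
- **Every magnitude is assumed, and inaccurate self-report affects the Yes/No item too.** This stands. The finding rests on the wording; the figures only show what could follow.
- **The plan already analyses the weekly texts.** Section 4.2.3 includes a GEE comparison of text-reported risk by arm, and the scripts shown use the defined wording. This is real mitigation, but as a secondary analysis. The primary outcome remains tied to the survey.
- **Controls simply continue the weekly assessments (section 2.13), so their wording is probably unchanged.** That is the natural reading. It still needs confirming, because no script is shown.
- **Section 4.2.3's rule for a missing week was written for gaps in both sources.** It does not clearly cover a survey responder who missed one text. This stands, so any text-only analysis must state the extension.

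None of these points reconciles the survey item with the definition.

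**Conclusion.** The concern holds. The plan contradicts itself: sections 2.14 and 3.1.1 promise the screening question, and both follow-up surveys contain a different one that cannot yield the defined outcome when the count is 3 or more. Missing surveys would be filled from a differently worded source.

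The bias cannot be sized from the documents. Under the assumed risks, cut-off and perfect sensitivity, a true 15-point difference would appear as 13.5 to 7.5 points for a common specificity of 0.9 to 0.5, and as 6.5 or 16.0 points in the two unequal-specificity examples. Equal misclassification dilutes the difference; unequal misclassification can push it either way.

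This is a should-fix. It affects the primary outcome of an exploratory cohort and leaves the powered Cohort 1 comparison untouched. The `control_dd` error is separate and minor, since it touches only Cohort 3's perceived-control comparison and an exploratory subgroup.

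**What to change.** 1. Put the screening Yes/No item, word for word and under the 2-week recall heading, into the 8-week and 14-week surveys, and score the Cohort 3 outcome from it. If the drink count is wanted, keep it under a different code.
2. Confirm that the control-arm texts and the texts for weeks 9 to 14 carry the 3-hour wording.
3. If follow-up has already used the count, state before unblinding which cut-off will be applied and that the result is a different, less specific measure than the defined outcome. Report the weekly text outcome over the same 2-week window, for all analysed participants in both arms, as a sensitivity analysis. Say explicitly that section 4.2.3's missing-week rule is extended to it. State its limit: during the intervention weeks only the intervention arm's answers trigger feedback, and participants are not blinded, so reporting at week 8 may differ by arm.
4. Minor: reword `control_dd` in the baseline, 8-week and 14-week surveys to ask about control over driving after drinking.

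The cost is one item restored in two surveys before follow-up starts and one item reworded in three surveys, the baseline one before enrolment. No participants or visits are added.

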Appendix: 14-Week Assessment

	The following questions ask you to recall times you have been in a car over the past 2 weeks.				
Questi on	How often have you driven a car?	Never	A few times	Most days	Every day
Code	driver	0	1	2	3
Questi on	How often did you wear a seat belt when you drove a car?	Never	A few times	Most of the time	Always
Code	drive_seatbelt	0	1	2	3
Questi on	How often have you been a passenger in the front seat of a car?	Never	A few times	Most days	Every day
Code	pass_front	0	1	2	3
Questi on	How often did you wear a seat belt when you were a passenger in the front seat ?	Never	A few times	Most of the time	Always
Code	pass_seatbelt1	0	1	2	3
	How often have you been a passenger in the back seat of a car?	Never	A few times	Most days	Every day
	pass_back	0	1	2	3
	How often did you wear a seat belt when you were a passenger in the back seat?	Never	A few times	Most of the time	Always
	pass_seatbelt2	0	1	2	3

Questi on	How often did you type on your phone while you were driving and when the car was moving?	Never	A few times	Most of the time	Always			
Code	distract	0	1	2	3			
Questi on	What's the most number of alcoholic drinks you've had prior to driving on any occasion?	#						
Code	drinks	#						
Questi on	Check off all the reasons you have not used a seat belt	Uncomfort able	Forgot	Don't think they help	Like freedom	Other	l alway s wear my seat belt	
Code	seatbelt_reasons	0	1	2	3	4	5	
Questi	If other, state reasons							
on								
Code	seatbelt_other							
Questi on	How often do your friends use their seat belt?	Never	Rarely	Most of the time	Always			
Code		0	1	2	3			
Questi on	How dangerous is it to not wear a seat belt?	Not at all	Somew hat	Very	Comple tely			
Code	danger_seatbelt	0	1	2	3			
Questi on	How much do you agree: I have complete control over whether I wear a seat belt.	Strongly Disagree	Disagre e	Somew hat Agree	Mostly agree	Stron gly Agree		
Code	control_sb	0	1	2	3	4		
Questi on	Check off all the reasons you have typed on your phone while driving?	l could not wait	l don't think it affects my driving	It was an emerge ncy	lt is fun	l get bored drivin g	l do not use my phon e while drivin g	l do not dri ve
Code	twd reasons	0	1	2	3	4	5	6
Questi on	How often do your friends type on their phones while driving?	Never	Rarely	Most of the time	Always			
Code		0	1	2	3			
Questi on	How dangerous is it to type on your phone while driving?	Not at all	Somew hat	Very	Comple tely			
Code	danger_twd	0	1	2	3			
Questi on	How much do you agree: I have complete control over whether I type on my phone while driving.	Strongly Disagree	Disagre e	Somew hat Agree	Mostly agree	Stron gly Agree		
Code	control_twd	0	1	2	3	4		
Questi on	Check off all the reasons you have driven a car after drinking alcohol?	l had no other opiton	l don't think it affects my driving	lt's not a big deal	l am careful	lt is fun	l do not drive after dirnki ng alcoh ol	l do not dri ve
Code	dd_reasons	0	1	2	3	4	5	6
Questi on	How often do your friends drive after drinking alcohol?	Never	Rarely	Most of the time	Always			
Code	friends_dd	0	1	2	3			
Questi on	How dangerous is it to drive soon after drinking more 3 or more alcoholic drinks?	Not at all	Somew hat	Very	Comple tely			
Code	danger_dd	0	1	2	3			
Questi on	How much do you agree: I have complete control over whether I type on my phone while driving.	Strongly Disagree	Disagre e	Somew hat Agree	Mostly agree	Stron gly Agree		
Code	control_dd	0	1	2	3	4		

SaVE Trial Protocol v.1.0 Page **35** of **36**

SaVE Trial Protocol v.1.0 Page **36** of **36**
